5.0 MONITORING PROCEDURES

Study staff at the University of Washington will be responsible for monitoring for data accuracy and completeness.

7.0 INFORMED CONSENT

Once an eligible participant is identified from UW or at external sites via REDCap screening survey, a UW research coordinator will call the patient and verbal consent will be obtained. Before obtaining verbal consent, UW study staff will review the consent form with participants, allow time to answer any questions, and ensure participants demonstrate an understanding of study requirements and agree to participate.

Study staff will ask the subject if they fully understand everything that was explained in the consent documents and if they have any questions. Consent documents will be emailed or mailed to subjects if additional information is requested before verbal consent is obtained. Subjects will also be provided with a copy of the consent document for their records which includes study staff contact information if they have additional questions.

Before obtaining verbal consent, all subjects will be told that this research study is voluntary and they are able to withdraw at any time. They will be given contact information of the study staff if they decide they would like to withdraw or if they have any questions pertaining to their involvement in the study.

8.0 IRB INFORMATION

This pilot RCT was reviewed and approved by the University of Washington Human Subject's Division IRB. Collaborating institution who distributed screening surveys for recruitment purposes were considered not engaged per HHS guidelines and did not require additional IRB approval from their local IRBs.

Any documents that the IRB may need to fulfill its responsibilities (such as protocol, protocol amendments, consent forms, information concerning patient recruitment, payment or compensation procedures, or other pertinent information) will be submitted to the IRB. The IRB's written unconditional approval of the study protocol and the informed consent form will be in the possession of the Investigator before the study is initiated.

Protocol and/or informed consent modifications or changes may not be initiated without prior written IRB approval except when necessary to eliminate immediate hazards to the patients or when the change(s) involves only logistical or administrative aspects of the study. Such modifications will be submitted to the IRB and written verification that the modification was submitted and subsequently approved should be obtained.

The IRB must be informed of revisions to other documents originally submitted for review; new information that may affect adversely the safety of the patients of the conduct of the study; an annual update and/or request for re-approval; and when the study has been completed.

10.0 ADDITIONAL RECORDS AND REPORTS

10.1 Data handling and record-keeping

All study data will be maintained using REDCap. Only authorized individuals will be permitted to access study data.

All investigators and staff involved will have completed human subjects' protection training, have HIPAA training, and be bound by the agreement of confidentiality. A copy of the protocol will be given to all study team members and regular meetings will be held to discuss matters including questions and responsibilities relating to the study. All study databases will be maintained at the UW on password protected computers and backed up to an encoded password protected file. All procedures for the handling and analysis of data will be conducted using good clinical practices meeting FDA guidelines for the handling and analysis of data for clinical trials.

10.2 Record maintenance and retention

This study will comply with records retention periods set by Washington State.

APPENDIX 1: Interview Guides

Overall Research Questions:

1. In what ways did the website(s) affect perceptions of preparedness to discuss transplant?
2. How well does ToT (stories/Resource Library/FAQ) or UNOS address the information needs of people living with CF? What information/information sources were meaningful, impactful, and salient (ToT or UNOS)?
3. What could be potential barriers and facilitators to using ToT or UNOS? What is the acceptability and feasibility of ToT (or UNOS)? How could ToT be improved?

Intro Session (prior to randomization) – 60-minute session

Goals of interview:

- Understand prior discussions and current understanding of LTx before exposure to the website(s) - what went well/not well during prior LTx discussions; has the participant thought about transplant; how could understanding be improved (information needs)?
 - Questions to complement survey responses - explore baseline preparedness for discussions; could the participant decide about LTx already?
 - Introduction to research website - 10 minute maximum plus demo video
1. Can you tell me about a time when you discussed lung transplant with your CF doctor?

If transplant has been discussed:

- Who initiated the conversation? If the patient initiated, why? If the doctor initiated, how did you react?
- What were some of the emotions you felt during the conversation?
- Did you feel prepared to have the conversation? Why/why not?
- Was anyone else present during the conversation? If yes, was it useful to have someone with you? If not, would you have preferred someone to be there?
- What could have made the conversation better?

If transplant has not been discussed:

- Has there ever been a time you wanted to discuss lung transplant with your doctor, but didn't? If yes, what stopped you from initiating the conversation?
- When do you think would be the right time to talk to your doctor about lung transplant?
- CF Foundation guidelines are now recommending people have annual conversations about transplant with their doctor once someone's FEV₁ is <50% predicted? In what ways might it be beneficial to talk about transplant early on? Could there be any harms or problems from discussing it too early?

2. Can you tell me about a time when you discussed lung transplant with a loved one (e.g friend or family member, etc.)?

If transplant has been discussed:

- How was this conversation similar or different from a conversation you might have with your doctor?
- How might you benefit from having these conversations with your loved one?

If transplant has not been discussed:

- If your loved one talked with you about lung transplant, how might you react?
- What might prompt you to talk about transplant with a loved one?

3. Do you know anyone who has received a lung transplant?

- If yes, how has knowing about transplant from recipients affected how you think of it?
- If no, how might hearing stories from people with CF who have undergone transplant affect how you think of it?

4. Can you tell me about any research you have done on lung transplant (for example, reading online or talking to others about it)?

If prior research:

- What prompted you to look into lung transplant?
- How was your experience looking for information about lung transplant?
- Did your doctor recommend or provide any resources to you?
- How did you discover other information sources?
- Did you trust the information you found? Why or why not?
- How informed do you think you are about lung transplant?
- Do you still have questions or concerns about transplant? If so, what are they?

If no prior research:

- How informed do you think you are about lung transplant?
- Where do you think you would start to look for information about lung transplant?
- What information would you look for?
- How might you benefit from learning about lung transplant?

5. What is your understanding of the timing of lung transplant for advanced CF?

- How did you come to understand the timing of transplant?
- What do you understand about how CFTR modulators (for example, Trikafta) play a role in the timing of transplant?

6. How ready do you feel to talk to your CF doctor about transplant? Why?

- What types of questions or concerns do you have about lung transplant?

7. Based on your conversations and/or research, how ready do you feel to make a decision about lung transplant?

If decision has been made:

- How did you come to make this decision?
- What might influence your decision, making you more or less certain?

If decision has not been made:

- What could help you make a decision?

- When do you think you need to make this decision?
- What might influence your decision?

Week 2 - 30-minute session

1. Can you tell me about how often you looked at the website over the past two weeks?
2. Did the reminders impact your interest in visiting the website? What did you think about the frequency of the reminders?
3. Was there anything that prevented you from using the website? If yes, can you walk me through them in more detail and discuss ways they could be addressed?
4. Can you tell me about any technical issues you may have experienced with the website or devices?
5. How satisfied are you with the amount of time you spent visiting the site over the past two weeks? Do you think there could be any value in returning at another time? What would you spend more time looking at? What might prompt you to return to the website again?
6. Now can you tell me some of your general opinions about the website? Why was or wasn't it engaging?
7. Can you give me an example of some topics you enjoyed reading about or topics you might have preferred to avoid?
8. Can you give me an example of information you might have found surprising? Why was it surprising to you?
9. How did the content in the website make you feel?
10. Do you think this website would be a good place to start your search for information about lung transplant for CF? Why or why not? Describe the questions about lung transplant that still remain after your use of this website.
11. Why might you recommend this website to others or not?
12. Do you think this would be a good website for your doctor to recommend?
13. Imagine you have an appointment tomorrow with your CF doctor, how prepared do you feel to discuss lung transplant after using this website? Why? (consider asking: why not [lower on Likert scale]? why not [higher on Likert scale]?)
14. How might you benefit from using the website with others (e.g. your doctor, friend, family)? Did you share any of the information on the website with others? If yes, what did you discuss?

Week 4 - 60 minute session

Goals of interview:

- Feasibility of use
- Preparedness for CF clinic visit
- Psychological impact
- Duration of RCT (4 weeks vs 3 months)

1. Can you tell me about how often you looked at the website over the past two weeks? Was there anything that prevented you from using the website, technical issues or something else? If yes, can you walk me through them in more detail and discuss ways they could be addressed?

2. How satisfied are you with the amount of time you spent visiting the sites over the past four weeks? Do you think there could be any value in returning to either site at another time? What would you spend more time looking at? What might prompt you to return to the websites again?
3. Can you compare your experience using the UNOS website to the Take on Transplant website?
 - Were you able to find information more easily in one website compared to the other? Can you give an example? What made it difficult to find the information you were looking for?
 - Did you find the information in the websites trustworthy? Why? Was there one website that was more or less reliable than the other?
 - Did one website help you feel more informed about lung transplant over the other?
 - Do you still have questions or concerns about transplant? If so, what are they and to which website would you choose to return to find answers? Why would you choose to return to one website over the other?
 - How often could you see yourself returning to the UNOS website? What about the Take on Transplant website?
 - Can you give me an example of something one website did better or worse than the other?
4. How did the content in the websites make you feel? Did one website evoke more or less of an emotional reaction than the other? If so, can you elaborate or provide an example?
 - Did you find any of the content distressing or disturbing?
 - Did you find yourself thinking about the content when you were not looking at the website? For example, were you thinking about information from the website when you were trying to work, read, or fall asleep?
 - Did the website impact your mental health? If yes, how?
5. Imagine you have an appointment tomorrow with your CF doctor, how prepared do you feel to discuss lung transplant after using the websites? How have they helped you feel more or less prepared to have a discussion with your CF doctor about lung transplant? As a reminder, two weeks ago you said you felt “XX” to have a discussion about lung transplant with your CF doctor? What are some things that changed or influenced this feeling? Was there one website that helped you to feel more prepared? Why/why not?

Shifting focus to the ToT website:

6. Can you tell me some of your general opinions on the three content areas (resource library, CF stories, and FAQs)?
 - a. How would you improve your experience with [each content area]?
 - b. Did you have any concerns with any of the content?
7. What did you think about the lung transplant discussion urgency meter?
8. Was the recommended content you received relevant to you? Why/why not?

9. Did the website suit your learning style? If not, why? What changes or additions could help? Would you prefer having the content in a different format (e.g. audio or video)?
10. Can you tell me about the CF stories you read? Why did you choose to read those stories? How did you relate or not relate to them? How do you think the CF stories might be similar or different to conversations you would have with transplant recipients?
11. How much of the content in ToT were you already familiar with (estimate a percentage)? Were you surprised by how much or how little you knew? Why/why not?
12. Do you think ToT could be used by individuals with CF at various stages of their health?
 - a. Why might you choose to use ToT when you are healthier?
 - i. What information would you look for?
 - ii. How could you benefit from using ToT?
 - iii. What would be the ideal amount of time for you to spend with the website?
 - b. What about when you are closer to needing a transplant?
 - i. What information would you look for?
 - ii. How could you benefit from using ToT?
 - iii. What would be the ideal amount of time for you to spend with the website?
13. In what ways could ToT help someone who is getting ready to talk to their doctor about lung transplant? How has it helped you feel more ready for these conversations?
14. Can you give some examples of topics you want to discuss with your CF doctor?
15. Would you have benefitted from using ToT with someone else like your doctor, a friend, or loved one? Did you get a chance to share anything from the site with anyone else?
 - a. What would be the ideal amount of time for you to have with ToT prior to an appointment with your CF doctor? Would you want to access ToT again after you visit with your CF doctor?
16. Why might you recommend this website to others or not?
17. Do you think this would be a good website for your doctor to recommend?
18. In what ways did ToT change what you know about lung transplant? Did it change any of your beliefs?
19. What are some advantages of using ToT over to other resources about lung transplant? In what ways could ToT supplement other resources about lung transplant?
20. Do you have any additional comments that you would like to share about your experience using ToT?

[If research website not used] Barriers to using the tool:

Please share the reasons you found it difficult to utilize the website.

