1.3. Objectives of the clinical investigation

1.3.1. Primary objective

The primary research objectives are to pilot test feasibility and efficacy of ToT to improve patient preparedness for decision making about LTx. The co-primary endpoint is feasibility, which will be defined successful by 90% of enrolled participants completing the 2-week study visit. A co-primary endpoint is an intention-to-treat assessment of the difference in mean PrepDM Scale in the intervention versus control arms of the study at the 2-week study visit.

1.3.2 Secondary objective(s).

The secondary objectives are to:

- Understand LTx knowledge gained.
- Assess changes in decisional conflict.
- Measure changes in preparedness for LTx discussions.
- Assess changes in depression and anxiety symptoms.
- Longitudinally characterize time spent using ToT through analysis of patient-level usage data and determine whether ongoing use of the tool is associated with maintaining or increasing ratings of preparedness at 1-month.
- Identify baseline demographic and health literacy predictors of increased ToT usage
- Analyze interview transcripts to inform revision of ToT prior to a large randomized controlled trial

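### Two Week 4 interview questions about Take on Transplant are worded one-sidedly (13 presumes it helped, 19 asks only for advantages), so the transcripts may under-record null or negative experience.

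*Combined protocol and SAP*

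**What the plan says.** Section 1.3.2 lists among the secondary objectives: "Analyze interview transcripts to inform revision of ToT prior to a large randomized controlled trial". Appendix 1 opens with overall research questions that cover both websites, for example "How well does ToT (stories/Resource Library/FAQ) or UNOS address the information needs of people living with CF", and the third of these ends by asking how ToT could be improved.

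The Week 4 guide has 20 numbered questions. Questions 1 to 5 deal with use of the websites, a comparison of UNOS with ToT, emotional reaction and preparedness. A line reading "Shifting focus to the ToT website" then introduces questions 6 to 20. The items at issue in that block are:

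- Question 12, sub-items a.ii and b.ii: "How could you benefit from using ToT", asked once for a healthier stage and once for a stage closer to transplant.
- Question 13, second sentence: "How has it helped you feel more ready for these conversations".
- Question 18, first sentence, which asks for the ways in which ToT altered the participant's knowledge.
- Question 19: "What are some advantages of using ToT over to other resources about lung transplant", followed by how ToT might add to those resources.

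The only direct request for criticisms is in the barriers module at the end of the appendix, which is reserved for participants who did not use the research website.

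**The concern.** A question that builds in its own answer is easier to agree with than to resist. A participant who felt no more ready after using ToT has to reject the premise of question 13 before answering it. A participant who found ToT worse than other sources in some respect is never asked about that at question 19. Both patterns favour acquiescence.

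What is at stake is the usefulness of the transcripts for revising ToT. Reports of no effect or an unwelcome effect are the most informative input to a revision, and these prompts are the least likely to draw them out. Section 2.6.1 describes ToT as investigator-designed, which is a further reason for neutral wording.

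**Working it through.** The plan gives no numerical target for the interviews, so the check is a count and a reading of the Week 4 questions.

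**Count.** The ToT block runs from question 6 to question 20, which closes the guide with "Do you have any additional comments that you would like to share about your experience using ToT". That is 20 − 6 + 1 = 15 questions, and 15/20 = 75%. Question 14, "Can you give some examples of topics you want to discuss with your CF doctor", is not about ToT. By content the count is therefore 14, and 14/20 = 70%.

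**Wording of the 15 questions in the block.**

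- Clearly one-sided: 2 (questions 13 and 19).
- Leaning the same way, more mildly: 2 (questions 12 and 18). Question 12 looks ahead to possible use at different stages of health and does not say that ToT worked. Question 18 presumes a change rather than a benefit, and its second sentence is an open yes/no question about beliefs.
- Borderline: 1 (question 15, whether using ToT together with someone else would have been of benefit).
- Explicitly open to negative answers or to improvement: 5 (question 6 on concerns and improvements; question 8 on whether the recommended content was relevant, and why or why not; question 9 on whether the site suited the participant's way of learning; question 10 on stories they did or did not relate to; question 16 on reasons to recommend or not).
- Neutral: 5 (questions 7, 11, 14, 17 and 20).

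The total is 2 + 2 + 1 + 5 + 5 = 15. One question asks for advantages and none asks for disadvantages.

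**Comparison with the rest of the appendix.** Elsewhere the guide asks in both directions. The introductory session asks about the benefits of early transplant discussion and then about possible harms. The Week 2 guide asks why the site was or was not engaging. Week 4 question 5 allows for feeling either better or worse prepared. Questions 13 and 19 depart from the guide's own practice.

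**The case against.** The strongest case on the other side is that the guide as a whole is reasonably balanced. Much of that case stands.

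- *The guide already lets people say that they were not helped.* Question 5 asks about preparedness in both directions for the two websites together, then whether one of them helped more, and why or why not. Question 4 asks about distress and mental health. Five questions inside the ToT block invite negative or improvement answers. This stands, and it limits the effect to under-eliciting such answers; they are not suppressed. It does not mend the two prompts themselves.
- *The share of ToT questions is no evidence of bias.* This stands. Transcripts gathered to revise ToT should concentrate on ToT, and the 70% or 75% shows focus, not slant.

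A reader might also infer three stronger points, which the documents do not support.

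- *That the comparison with UNOS is one-sided.* It rests mainly on questions 3 to 5, which are even-handed and come before the ToT block, so later prompts cannot colour those answers if the guide is followed in order. The Week 4 guide has no UNOS-only block, but the 14 questions of the Week 2 guide put the same items to each arm about its assigned site, so control participants give a full UNOS interview.
- *That the prompts distort the PrepDM score at the 4-week visit.* The order of survey and interview is not fixed: section 2.5.2 describes surveys first, and the table in section 2.5.9 lists the interview first. Carry-over is therefore conjecture. Both arms receive the same Week 4 guide, so no bias in the between-arm difference is shown.
- *That the designers of ToT conduct the interviews.* Section 2.5.8 identifies the interviewer only as research staff of the coordinating university.

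**Conclusion.** The concern holds for the wording of two prompts. Question 13 presumes benefit, and question 19 asks for advantages without disadvantages. Question 12 (two sub-items) and the first half of question 18 share the tendency to a lesser degree. That is 2 of 20 Week 4 questions clearly one-sided, or 4 of 20 with the milder ones.

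The consequence is some under-recording of null or negative experience in transcripts meant to guide revision of ToT. Its extent cannot be worked out from the documents. The conclusion assumes that interviewers follow the guide largely as written; an interviewer who probes freely in both directions would reduce the effect.

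Neither co-primary endpoint is touched. Completion of the 2-week visit and the 2-week PrepDM score are both settled before a participant reaches the Week 4 interview. This is a minor point that is worth correcting because the correction is nearly free.

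**What to change.** Reword two questions in place:

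- Question 13, second sentence: *Did ToT leave you feeling more ready, less ready or no different for these conversations? Why?*
- Question 19, first sentence: *What are the advantages and disadvantages of ToT compared with other resources, including UNOS?*

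Optionally, make the milder items two-sided as well:

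- Question 12, a.ii and b.ii: *What, if anything, would you gain or find unhelpful?*
- Question 18: *Did ToT change what you know or believe about lung transplant, or not? How?*

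There is no need to repeat these questions for UNOS, since questions 3 and 5 largely cover that ground. This point gives no ground for a new rule on the order of survey and interview.

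The cost is a few wording edits and at most a few minutes of a 60-minute interview, with no change to sample size, visits or analysis. Because the guide is an appendix to the protocol, the edit would go to the IRB under section 8.0 unless it counts as logistical or administrative.
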